5.4 Treatment Administration

Patients who are randomized to receive Vitamin A may start no later than 3 months from the time of registration in a time frame that allows them to have surgery with 10 days of completing treatment Vitamin A treatment. Vitamin A will be administered at 10,000 IU orally for 7 consecutive days. Surgery may occur on the day that the last Vitamin A dose is taken. If surgery is delayed more than 21 days from completing Vitamin A, the patient will be considered non-evaluable and will be replaced.

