Vitamin A and other retinoids function by activating nuclear receptors including retinoic acid receptors (RARs) and retinoid X receptors (RXRs) [3, 6, 7]. Activation of these nuclear receptors leads to transcription of target genes and changes in cellular function. Several lines of evidence support an important role for vitamin A to support immune system function. Vitamin A deficiency increases risk of infections in experimental models. Also, vitamin A supplementation reduces mortality from infectious complications in populations with a high risk of deficiency. Furthermore, vitamin A supplementation has been shown to improve antibody titers in response to vaccination in clinical trials.

The mechanisms through which vitamin A promotes immune system function are complex and involve both B-cell and T-cell mediated effects. The focus of the current study will be to examine changes in B-cell function although T-cell subsets will also be examined. In published studies from preclinical models, retinoid treatment of B-cells has been shown to increase cellular proliferation, improve antibody diversification through somatic hypermutation, and increase immunoglobulin production. In addition, animal models have shown that retinoid treatment increases formation of germinal centers which are critical for B-cell maturation.

Given the opportunities to improve patient outcomes by improving immunologic function, investigation of vitamin A supplementation in patients with lung cancer is an exciting opportunity to investigate an immunologic active treatment with minimal toxicities. Vitamin A treatment side effects can occur following prolonged exposure to very high doses but are extremely uncommon with shorter courses of treatment. Changes in cellular function, however, are quite rapid with target gene expression changes occurring within 24 hours. Increases in germinal center (GC) formation triggered by retinoids are seen in animal models following 6 days of retinoid treatment with measurements performed on day 10 (4 days after completing retinoid treatment) [15]. For this study we will examine a 7-day period of treatment with vitamin A in a window-of -opportunity neoadjuvant setting.

In our study, we will examine clinical outcomes including pathologic response and overall survival. The rational for induction of GC formation improving outcomes arises from an early study of resected lung cancers found that primary lung cancers with GC

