3.0 Patient Selection

3.1 Inclusion Criteria

- 3.1.1 Patient must be \geq 18 years of age
- 3.1.2 Patients must have either biopsy proven or radiographically suspected non-small cell lung cancer.
- 3.1.3 Patients must have disease in the chest that is felt to be surgically resectable.
- 3.1.4 ECOG performance status of 0-2.
- 3.1.5 Ability to understand and the willingness to sign an IRB-approved informed consent document

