11.2 Method of Randomization

Patients will be randomized in a 1:1 ratio to receive the vitamin A treatment intervention or standard of care. Patients will be stratified for randomization based on pre-operative stage (stage 1, 2, or 3).

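### Surgery-timing and late-surgery exclusion rules apply only to the vitamin A arm, and nothing before assignment checks that planned surgery leaves room for the 7-day course

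*Combined protocol and SAP*

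**What the plan says.** Section 5.4 (Treatment Administration) is the only place in the available text that times surgery, and each rule there is tied to vitamin A:

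- Start: "Patients who are randomized to receive Vitamin A may start no later than 3 months from the time of registration".
- Planned interval to surgery: "in a time frame that allows them to have surgery with 10 days of completing treatment".
- Course: "Vitamin A will be administered at 10,000 IU orally for 7 consecutive days".
- Earliest surgery: "Surgery may occur on the day that the last Vitamin A dose is taken".
- Late surgery: "If surgery is delayed more than 21 days from completing Vitamin A, the patient will be considered non-evaluable and will be replaced".

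For the comparator, section 11.2 says only "Patients will be randomized in a 1:1 ratio to receive the vitamin A treatment intervention or standard of care". Stratification is by pre-operative stage.

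On surgery, section 3.1 requires only this: "Patients must have disease in the chest that is felt to be surgically resectable". The eligibility checklist (Appendix B) and the registration form (Appendix A) have no field for a planned surgery date, and under section 4.0 the registrar then assigns the arm. The primary outcome (section 5.1) is presence or absence of germinal centers in the resected cancer.

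**The concern.** Randomization makes the arms comparable at assignment. That comparability carries through to the result only if both arms are followed to resection, and kept in the analysis, under the same rules. Here one arm must fit a course in before surgery and can lose patients to a late-surgery rule. The other has neither condition.

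Two consequences follow. First, short-notice patients are handled differently by arm, and the plan does not say how a vitamin A patient is classified if surgery arrives before the seventh dose. Secondly, removal and replacement for late surgery can happen only in the vitamin A arm, after randomization. Patients whose surgery is delayed may differ from the rest, and their counterparts in the control arm stay in. The outcome is read once, with no baseline reading, so the data cannot separate these effects from that of the drug.

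**Working it through.** **1. The rules side by side**

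| Question | Vitamin A arm | Control arm |
|---|---|---|
| Earliest surgery | Day of last dose, i.e. dosing day 7 for a full course (5.4) | None stated |
| Planned limit after treatment | 10 days (5.4) | Not applicable |
| Latest evaluable surgery | 21 days after completion (5.4) | None stated |
| Removed and replaced if surgery is late | Yes (5.4) | No rule |
| Surgery date checked before assignment | No (3.1, 4.0, Appendices A and B) | No |

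The visit table in section 5.3 names its middle visit by completion of vitamin A, which gives controls no anchor either.

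**2. The dates that section 5.4 implies**

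Take registration as day 0 and 3 months as about 91 days (assumption). With the first dose on day 91, the seventh falls on day 91 + 6 = 97.

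- Latest surgery on the 10-day statement: 97 + 10 = day 107.
- Latest evaluable surgery on the 21-day statement: 97 + 21 = day 118.
- Control arm: no lower or upper limit.

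The two statements differ by 21 − 10 = 11 days. A patient operated on 11 to 21 days after the course misses the first and satisfies the second. The text does not say how they relate.

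**3. One patient followed through both arms**

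Take a hypothetical patient whose operation is 3 days away at registration. Nothing in 3.1 or Appendix B prevents enrolment. In the control arm, the patient is operated on and counted. In the vitamin A arm, either surgery moves or the course is incomplete. Section 6.2.1 deals with side effects and withdrawal of consent, and section 6.4 lists reasons for stopping. Neither covers surgery arriving before the course is finished.

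**4. Scale, as illustration only**

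The plan's own figure first. With 90 per arm, 35% against 53% and one-sided alpha 0.05 (section 11.1):

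power = Φ[(Δ − 1.645 × SE₀) / SE₁]

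- Δ = 0.53 − 0.35 = 0.18
- SE₀ = √(2 × 0.44 × 0.56 / 90) = 0.0740
- SE₁ = √((0.35 × 0.65 + 0.53 × 0.47) / 90) = 0.0728

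This gives 78.8% (79.6% with unpooled variance), close to the stated 80%, which is not in dispute.

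The documents give no effect of scheduling or exclusion on germinal center rates. The shifts below are therefore assumed, in either direction:

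| Assumed shift in vitamin A arm | Rejection rate, no drug effect, rate raised above 35% | Power, rate lowered from 53% |
|---|---|---|
| 2 points | 8.6% | 70% |
| 5 points | 17% | 55% |
| 8 points | 29% | 39% |
| 10 points | 39% | 29% |

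The table shows how sensitive the test would be to such a shift. It is not evidence that one exists.

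**The case against.** The best defence is that section 5.4 places the course within the wait for surgery and does not move surgery to suit the course: it allows up to 3 months to start and ties the start to a feasible surgery date. If the usual wait exceeds a week, the arms need not differ in time to resection. This stands. The documents give no waiting times, and the short-notice patient is hypothetical.

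Four stronger readings are tempting, and the documents do not support them.

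- A reader might infer that treatment is confounded with time to surgery. That interval arises after randomization, so it is not a baseline confounder. A delay caused by giving the course is part of the assigned strategy.
- A reader might infer an enforced gap of about 6 days (day 7 against day 1). That compares the earliest possible dates. A patient in each arm could have surgery on day 30.
- A reader might infer from section 1.0 that waiting itself alters the outcome, since it says "Changes in cellular function, however, are quite rapid with target gene expression changes occurring within 24 hours". That sentence, and the animal germinal center data beside it, concern retinoid treatment. No section says that untreated waiting changes germinal centers or necrosis.
- A reader might want time to surgery added to the logistic model in section 11.3. Assignment can affect that variable, so adjusting for it may introduce bias.

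Nor is the interval unknowable. Appendix A records registration and treatment-start dates, Appendix L records dose dates, and a surgery date should be in the operative record. What is missing is a labelled field on the outcomes form.

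None of this answers the one-sided removal rule, which is explicit in section 5.4 and needs no assumption about waiting.

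**Conclusion.** The asymmetry is real. On the available text, all surgery-timing and late-surgery evaluability rules apply to the vitamin A arm alone, and no step before assignment confirms that the course can be completed before planned surgery. The primary contrast therefore estimates the drug effect plus any arm-specific difference in scheduling and exclusion.

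The size and direction of that addition cannot be derived from the documents, and it may be negligible. The case for change rests on the low cost of prevention, not on a demonstrated bias. The conclusion assumes that the schema figure and the few pages not available contain no timing rule for controls.

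**What to change.** 1. Before the registrar assigns the arm, confirm for every patient that the planned surgery date accommodates the course already described in section 5.4. Add this line to section 3.1 and Appendix B.
2. Count any timing-based evaluability rule from registration or randomization and apply it identically to both arms. Alternatively, keep all randomized and resected patients in the primary analysis. Either removes the one-sided exclusion.
3. Add a labelled date of surgery to Appendix F for both arms, and report registration-to-surgery time by arm descriptively.
4. Reconcile the 10-day and 21-day statements in section 5.4. No window is proposed here.

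Cost: one eligibility line, one form field, an edit to section 5.4 and a descriptive table. The real downside is that short-notice surgical patients are lost from both arms, which may slow accrual below the planned 90 per year by an amount the documents do not allow one to estimate.

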2.0 Objectives

2.1 Primary Objective

- 2.1.1 To compare the percentage of resected cancers containing germinal centers (GCs) in patients who receive neoadjuvant vitamin A to controls.

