5.0 Study Outcomes and Study Measures

5.1 Primary Outcome

5.1.1 Presence/absence of germinal centers (GCs) in resected cancer tissues from patients who receive neoadjuvant vitamin A and controls.

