6.2.1 Dose Modifications

No dose modifications will be performed. Patients who have unacceptable side effects or withdraw consent prior to undergoing surgical resection will discontinue treatment, considered non-evaluable, and will be replaced.

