11.3 Analysis of Primary Objective

11.3.1 The outcome for our primary objective is dichotomous—GCs present/absent. Following basic bivariate analysis in contingency tables of presence/absence by treatment arm we will model presence/absence of GCs in a logistic regression model as a function of treatment arm, stage, and age at diagnosis. We will first examine the statistical interaction term between stage and treatment arm, and if it is significant, we will present findings stratified by stage. If it is not significant, we will remove the interaction term from the final model and include stage as a simple covariate only.

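### Two post-randomisation rules remove and replace patients in the vitamin A arm only, and Section 11 names no analysis set for the germinal-centre comparison.

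*Combined protocol and SAP*

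**What the plan says.** Section 5.4 (Treatment Administration) asks that vitamin A be started "in a time frame that allows them to have surgery with 10 days of completing treatment Vitamin A treatment". It then sets an evaluability rule: "If surgery is delayed more than 21 days from completing Vitamin A, the patient will be considered non-evaluable and will be replaced".

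Section 6.2.1 (Dose Modifications) adds: "Patients who have unacceptable side effects or withdraw consent prior to undergoing surgical resection will discontinue treatment, considered non-evaluable, and will be replaced".

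Section 11.2 describes the comparison: "Patients will be randomized in a 1:1 ratio to receive the vitamin A treatment intervention or standard of care". No surgery-timing rule counted from registration or randomisation is given for controls.

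Section 11.3 gives the primary model, "we will model presence/absence of GCs in a logistic regression model as a function of treatment arm, stage, and age at diagnosis", after simple contingency tables. Sections 11.1 to 11.7 cover power, randomisation, models and accrual. None of them names an intention-to-treat, modified or evaluable population, or says what happens to the data of a replaced patient.

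The objective in Section 2.1 is "To compare the percentage of resected cancers containing germinal centers (GCs) in patients who receive neoadjuvant vitamin A to controls", and the outcome in Section 5.1 is read "in resected cancer tissues from patients who receive neoadjuvant vitamin A and controls". Section 6.5 follows patients to death for survival.

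**The concern.** A randomised comparison needs the same inclusion rule in both arms. Here, two patients with the same surgical delay are treated differently: the one given vitamin A is removed and replaced, and the control is kept. The side-effect trigger is not written as arm-specific, but controls take no study drug, so in effect they cannot meet it. Consent withdrawal, in the same sentence of Section 6.2.1, can occur in either arm and is not part of this point.

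Neither trigger prevents resection or a GC reading, so the results at issue can often be obtained. If the removed patients have a different GC rate from the rest, dropping them shifts the vitamin A arm and leaves the control arm untouched. The same silence affects overall survival, because the plan does not say whether a replaced patient still counts.

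**Working it through.** **Inputs from Section 11.1:** 90 patients per arm, one-sided alpha 0.05, GC rate 35% in controls and 53% with vitamin A (18 points), stated power 80%.

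**Assumptions, not in the documents:** the fraction f of the vitamin A arm removed, and the GC rate q among those removed.

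**Method:** unadjusted two-proportion z test, with pooled standard error under the null and unpooled under the alternative.

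**1. The plan's own figure.** Power = Φ[(d − 1.645 × SE0)/SE1]. With d = 0.18, the mean rate is 0.44.
- SE0 = √(2 × 0.44 × 0.56/90) = 0.0740
- SE1 = √((0.35 × 0.65 + 0.53 × 0.47)/90) = 0.0728
- Power = 78.8% (79.6% if the unpooled error is used throughout)

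The stated 80% is reproduced to within about a point and is not in dispute.

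**2. Error rate if removed patients are dropped and replaced.** Suppose there is no true effect, so 35% of all randomised patients in each arm have GCs. The retained vitamin A rate is r = (0.35 − f × q)/(1 − f). For f = 10% and q = 20%, r = (0.35 − 0.02)/0.90 = 36.7%. The table gives the chance of a one-sided positive result for r against 35%, with 90 retained per arm.

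| Removed (f) | r, q = 20% | Error, q = 20% | Error, q = 35% | r, q = 50% | Error, q = 50% |
|---|---|---|---|---|---|
| 1% | 35.15% | 5.2% | 5.0% | 34.85% | 4.8% |
| 2% | 35.31% | 5.5% | 5.0% | 34.69% | 4.6% |
| 5% | 35.79% | 6.2% | 5.0% | 34.21% | 4.0% |
| 10% | 36.67% | 7.9% | 5.0% | 33.33% | 3.0% |
| 15% | 37.65% | 10.1% | 5.0% | 32.35% | 2.2% |

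The shift in the vitamin A rate is 0.15 × f/(1 − f), that is 0.8, 1.7 and 2.6 points at 5%, 10% and 15% removed. The planned effect is 18 points.

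**3. Power if these patients are kept.** Suppose they have only the 35% background rate. The vitamin A rate is then t = 0.53(1 − f) + 0.35f. Power is given for 90 against 90, and for the case where they are kept and also replaced, so that the vitamin A arm has 90/(1 − f) patients against 90 controls.

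| f | t | Power, 90 v 90 | Vitamin A arm if also replaced | Power if also replaced |
|---|---|---|---|---|
| 0% | 53.0% | 78.8% | 90 | 78.8% |
| 1% | 52.8% | 78.1% | 90.9 | 78.3% |
| 2% | 52.6% | 77.4% | 91.8 | 77.8% |
| 5% | 52.1% | 75.1% | 94.7 | 76.1% |
| 10% | 51.2% | 71.1% | 100 | 73.0% |
| 15% | 50.3% | 66.8% | 105.9 | 69.7% |

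**4. Which rows are plausible?** Section 1.0 describes vitamin A side effects as very rare with short courses, so the low rows fit the side-effect trigger. Surgery is planned within 10 days of the last dose, so the 21-day rule catches only slippage of more than 21 − 10 = 11 days beyond that. No section gives its frequency.

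**The case against.** The strongest reply is that the harm is inferred. No sentence says that an available GC reading is discarded, and replacement could be only an accrual rule to protect 90 per arm. That is a possible reading. However, calling a patient non-evaluable goes further than accrual, and nothing in Section 11 overrides it. If the sponsor means to keep the readings, the text has to say so.

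Second, this is a pilot, short-exposure biological study whose objective speaks of patients who receive vitamin A. An evaluable-patient analysis with a limit on time since the last dose would suit that question. This stands in part: such a set may be intended. But the plan neither defines it nor gives controls an equivalent rule.

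Third, the bias may be trivial. At 1% to 2% removed, even a 15-point gap moves the error only to between 4.6% and 5.5%. The larger figures need both 10% to 15% removal and a link between removal and GC status, and the documents support neither. This stands, and it limits the claim to a possible bias of unknown size.

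Fourth, the proposed primary set still depends on resection and histology, both known only after randomisation. That is true, but the rule is then the same in both arms.

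**Conclusion.** The concern holds. Two things are clear from the text: both removal rules operate in the vitamin A arm only, and no analysis set is defined for the primary comparison or for survival. A material bias is not shown. Its direction and size depend on the removal rate and on the GC rate of removed patients, which the documents do not give. Under the assumptions used, the error rate ranges from 2.2% to 10.1% against a nominal 5%, and stays at 5.0% if removal is unrelated to GC status. The point should be fixed because the repair is cheap and settles the denominator in advance.

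**What to change.** Change the analysis wording only; dosing and surgery timing are untouched.

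1. **Primary GC set:** all randomised patients with resected NSCLC tissue, analysed as assigned whatever the doses taken, side effects or interval to surgery, subject to any withdrawal of consent for data use. State that this is an as-randomised comparison, although Sections 2.1 and 5.1 refer to patients who receive vitamin A.
2. **Overall survival:** all randomised patients, including those replaced. Censor withdrawals at the point where data use ends.
3. **Existing 21-day and side-effect exclusions:** keep them only for a labelled per-protocol sensitivity analysis.
4. **Reporting, separable from the core fix:** give by arm the number excluded and the number without resected NSCLC. The second count is needed because Section 3.1 says "Patients must have either biopsy proven or radiographically suspected non-small cell lung cancer", so some patients may prove not to have NSCLC. Restrict the sensitivity analysis for missing GC status (all absent, all present, opposite values by arm) to patients with NSCLC, since tumour GC status is undefined for the others.

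The cost is protocol and SAP wording, two sensitivity analyses, and the dilution shown above: at 5% affected, power is 75.1%, or 76.1% if those patients are kept and also replaced; at 10% it is 71.1% or 73.0%; at 15% it is 66.8% or 69.7%.

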6.2.1 Dose Modifications

No dose modifications will be performed. Patients who have unacceptable side effects or withdraw consent prior to undergoing surgical resection will discontinue treatment, considered non-evaluable, and will be replaced.

6.3 General Concomitant Medication and Supportive Care Guidelines

Patients should receive *full supportive care*, including transfusions of blood and blood products, erythropoietin, antibiotics, antiemetics, etc., as clinically indicated. Anti-inflammatory or narcotic analgesics may be offered as needed. Medications considered necessary for the patient's well-being may be given at the discretion of the investigator, i.e., chronic treatments for concomitant medical conditions, as well as agents required for life-threatening medical problems, etc. The reason(s) for treatment, dosage, and dates of treatment should be recorded on the flow sheets.

6.4 Duration of Therapy

Treatment will continue for 7 days. In the absence of treatment delays due to adverse events, treatment may continue until one of the following criteria applies:

- Disease progression,
- Intercurrent illness that prevents further administration of treatment,
- Unacceptable adverse event(s), specifically if Grade 3 or 4 toxicity is observed
- Patient decides to withdraw from the study, or
- General or specific changes in the patient's condition render the patient unacceptable for further treatment in the judgment of the investigator.

6.5 Duration of Follow Up

Patients will be followed for a minimum of 30 days after the last study drug is administered for adverse events monitoring. Patients will be followed for a minimum of 30 days after removal from study or until death, whichever occurs first. Patients removed from study for unacceptable adverse events will be followed until resolution or stabilization of the adverse event. Patients will be followed until death for monitoring survival study endpoints.

